6.8.1.1. Adverse Events of Special Interest

Adverse events of special interest (AESI) include the following events:

- CRS: PT coded as “cytokine release syndrome” and collected on the AE CRF page;
- ICANS: PT coded as “immune effector cell-associated neurotoxicity syndrome” and collected on the AE CRF page;
- Peripheral neuropathy: Standardized MedDRA Queries (SMQ) Peripheral Neuropathy (narrow and broad excluding PTs included in the Guillain-Barre syndrome SMQ) and Guillain-Barre syndrome SMQ (narrow).

CRS and ICANS will be assessed according to ASTCT criteria. All the analyses will be performed by each individual AESI separately.

A high-level summary of each AESI will include the number and percent of participants with, separately:

- Any AESI;
- Serious AESI;
- AESI by maximum toxicity grade;
- Had >1 AESI (for CRS and ICANS only);
 - Note: If there are >1 AESI with different grades between the two doses, it will be considered as one AESI.
- Had ICANS concurrent with CRS (for ICANS only). Note: if both CRS and ICANS occurred between the same two doses they will be considered as concurrent;
- AESI leading to dose interruptions;
- AESI leading to dose reductions;
- AESI leading to dose interruptions or reductions;
- AESI leading to permanent discontinuation of study intervention;
- AESI with outcome as resolved (for peripheral neuropathy only).

In addition, the following summary will be provided with descriptive statistics (mean, median, standard deviation, minimum, and maximum) as well as broken down in categories by the time to onset and resolution of the AESI:

- Time to onset of the AESI;

- Time to resolution of the AESI).
- Duration of each AESI event.

For CRS and ICANS, time relative to dose (ie, after the first dose, after the second dose, after >2 doses) will also be summarized with descriptive statistics (mean, median, standard deviation, minimum, and maximum).

A summary of AESI symptoms will be provided as follows. The most severe symptom will be summarized if participants have multiple occurrences of AESI symptoms.

- The CRS symptoms as collected on the ‘CRS AE’ CRF will be summarized by symptom grade using frequency counts and percentages;
- The ICANS symptoms as collected on the ‘ICANS’ CRFs will be summarized using frequency counts and percentages;
- The ICE scores as collected on the ‘ICE’ CRFs will be summarized for those participants with ICANS events based on the total ICE scores as follows:
 - ICE score 10;
 - ICE score 7-9;
 - ICE score 3-6;
 - ICE score 1-2;
 - ICE score 0.

In addition, the number and percent of participants with CRS/ICANS who received tocilizumab/ steroids (from Conmed CRF) will be summarized.

For peripheral neuropathy, the following summary will be provided:

- Peripheral neuropathy TEAEs by PT and maximum severity grade (all causality and treatment-related);
- Peripheral Neuropathy TEAEs (all causality) and Medical History.

A listing of AESI with supportive information will also be provided.

6.8.1.2. Other Adverse Events of Clinical Interest

Other adverse events of clinical interests (oAECIs) include the following events:

- Infections:
 - The MedDRA SOC of Infections and infestations.

- Cytopenias:
 - The MedDRA PTs for cytopenia are defined in the Appendix ([Section 9.1](#)).
- Injection site reactions:
 - The MedDRA HLT of Injection site reactions.
- Hypogammaglobulinemia
 - Including the MedDRA PTs: Blood immunoglobulin G decreased, Hypogammaglobulinaemia, Hypoglobulinaemia, Immunoglobulins decreased and Globulins decreased.

All the analyses will be performed by each individual oAESI separately. For cytopenias, the individual PTs (ie, not clustered terms) will be reported in the summary.

A high-level summary of each oAECI will include the number and percent of participants with:

- Any oAECIs;
- Serious oAECIs;
- oAECIs by maximum toxicity grade;
- oAECIs leading to dose interruptions;
- oAECIs leading to dose reductions;
- oAECIs leading to dose interruptions or reductions;
- oAECIs leading to permanent discontinuation of study intervention;

The following summary will be provided for each oAESI:

- oAECI by PT and maximum severity grade (all causality and treatment-related);
- Time to onset of the oAECI and time to resolution of the oAECI with descriptive statistics (mean, median, standard deviation, minimum, and maximum).

A listing of oAECIs with supportive information will also be provided.

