**Table 14. Protocol Required Safety Laboratory Assessments (locally performed)**

Hematology	Chemistry	Other

 
Hemoglobin
 
Platelet count
 
WBC count
 
Plasma cell count
 
 
Absolute:
 
 
Neutrophils
 
Eosinophils
 
Monocytes
 
Basophils
 
Lymphocytes
 
Plasma cells
 
 
Database should be constructed to allow capture of WBC differential counts as percent and absolute values but only 1 or the other should be used by the site to collect data. Results will be reported as absolute values after conversion and graded according to the CTCAE criteria
	
 
BUN (or blood urea)
 
Creatinine
 
Glucose (non-fasting)
 
Total Calcium
 
Sodium
 
Potassium
 
Chloride
 
Magnesium
 
Phosphorus or Phosphates
 
AST, ALTc
 
Total bilirubin
 
Alkaline phosphatase
 
Albumin
 
Chloride
 
Total CO2 (bicarbonate)
 
Total Protein
 
Lactate dehydrogenase (LDH)a
 
Uric acida
 
Serum beta-2 microglobulina,d
 
	
 
CMV by quantitative PCR
 
PT/INR
 
For female participants of childbearing potential Pregnancy test (β-hCG)b
 
HBV tests (HBsAg and HBcAb, HBsAb)eHCV Abe
 
SARS-CoV-2 testingf
 

- At baseline (minimum) and as clinically indicated.
- For female participants of childbearing potential only. Serum test is required at screening; for other time points, urine testing will be standard for the protocol unless serum testing is required by local regulation or IRB/EC.
- For Hy's law potential cases, in addition to repeating AST and ALT, laboratory tests should include albumin, creatine kinase, total bilirubin, direct and indirect bilirubin, gamma-glutamyl transferase, prothrombin time (PT)/INR, and alkaline phosphatase.
- Required for multiple myeloma staging.
- To be performed at screening or as clinically indicated per PI assessment throughout study period. In the case of apparent ongoing HBV or HCV infection, reflex serum DNA or RNA viral load testing, respectively, will be performed if required by local regulation.

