5.2. General Methods

Unless otherwise specified, all efficacy analyses and safety analyses will be performed using the Safety Analysis Set. All analyses will be performed by part as follows:

- Part 1;
- Part 2;
 - Part 2A Dose level 1 (if Dose level 2 is identified as RP2D);
 - Part 2A (RP2D) + Part 2B;
 - CCI
- Part 1 and Part 2 Combined.

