5.2.13. Analyses for Continuous and Qualitative Variables

Continuous variables will be summarized using descriptive statistics ie, number of non-missing values and number of missing values [ie, n (missing)], mean, median, standard deviation, minimum, maximum and first and third quartile (Q1 and Q3).

Qualitative variables will be summarized by frequency counts and percentages. Unless otherwise specified, the calculation of proportions will include the missing category. Therefore, counts of missing observations will be included in the denominator and presented as a separate category.

In case the analysis refers only to certain visits, percentages will be based on the number of participants still present in the study at that visit, unless otherwise specified.

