6.7.3. Study Intervention Exposure

Exposure will be summarized based on the Safety Analysis Set.

Elranatamab is administered as a subcutaneous injection. For both Part 1 and Part 2, 2 step-up priming doses regimen will be used during the first cycle as following:

- **C1D1:** Premedication + elranatamab 4 mg;
- **C1D4:** Premedication + elranatamab 20 mg;
- **C1D8:** Premedication + elranatamab 76 mg;
- **C1D15 and C1D22:** elranatamab 76 mg QW.

Starting from Cycle 2, the following dosing regimens will be assessed:

- **Part 1** will evaluate full elranatamab doses at 76 mg QW from Cycle 2 to Cycle 6. Starting from Cycle 7, the dose interval will be changed from QW to Q2W in participants with IMWG response of PR or better persisting for ≥ 2 month on QW. **Once the RP2D is identified in Part 2A**, the dose interval would also be the elranatamab RP2D (116 mg or 152 mg) Q4W in participants with IMWG response of PR or better persisting for ≥ 2 months on QW or Q2W.
- **Part 2A** will evaluate full elranatamab doses at 116 mg Q2W (**Dose level 1**) and 152 mg Q2W (**Dose level 2**) from Cycle 2 to Cycle 6. Starting from Cycle 7, the dose interval will be changed from Q2W to Q4W in participants with IMWG response of PR or better persisting for ≥ 2 month on Q2W.
- **Part 2B** will evaluate the potential RP2D from Part 2A (**Dose level 1** or **Dose level 2**) from Cycle 2 to Cycle 6 at Q2W dosing interval. Starting from Cycle 7, the dose interval will be changed from Q2W to Q4W in participants with IMWG response of PR or better persisting for ≥ 2 month on Q2W.

- CCI

For both Part 1 and Part 2, if, after switching to a less frequent dosing interval, the participant subsequently begins to have an increase of disease burden not yet qualifying as PD according to IMWG criteria, dose intervals should return to the previous dose interval for the remainder of the study.

The summary of treatment exposure to elranatamab will include the following information:

- Treatment duration (weeks);
- Number of cycles started per participant (mean, median, min, max);
- Number and percent of participants starting a cycle (any cycle, cycle 1, 2, 3, 4, 5, 6, 7, 8, 9, 10, 11, ≥ 12 cycles);
- Total cumulative dose (mg);
- Overall dose intensity (mg/week);
- Overall relative dose (%);
- Overall relative dose intensity (%);
- Number and percent of responding participants after 6 cycles who switched from QW to Q2W or Q4W (Part 1) or from Q2W to Q4W (Part 2);

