For calcium, CTCAE grading is based on Corrected Calcium and Ionized Calcium. Corrected Calcium is calculated from Albumin and Calcium as follows:

$$\text{Corrected Calcium (mg/dL)} = \text{measured total calcium (mg/dL)} - 0.8 [\text{serum albumin (g/dL)} - 4]$$

Creatinine clearance is calculated as follows:

- Male: Creatinine Clearance = $((140 - \text{Age}) / (\text{Serum Creatinine})) * (\text{Weight} / 0.814)$;
- Female: Creatinine Clearance (eGFR) = $0.85 * ((140 - \text{Age}) / (\text{Serum Creatinine})) * (\text{Weight} / 0.814)$.

Note: the SI unit of Serum Creatinine is "micromol/L", the unit of weight is "Kg".

Abnormalities will be described using the worst grade by scheduled timepoint and overall. Worst case overall will be determined using laboratory results from scheduled and unscheduled visits. Several laboratory tests have bi-directional grading criteria defined so that both low (hypo) and high (hyper) values can be graded separately. Each criterion will be summarized separately. In the cases where a value is graded as a Grade 1, 2, 3, or 4 for one of the directions, that value will also be assigned as a Grade 0 for the opposite direction for that test. For example, a value meeting the criteria for Grade 3 Hypercalcemia will be classified as a Grade 0 Hypocalcemia. For CTCAE terms that can be derived using one of several laboratory tests, the maximum postbaseline grade for a given participant and CTCAE term will be the maximum across all possible laboratory tests.

Additional laboratory results that are not part of NCI-CTCAE will be presented according to the following categories by scheduled timepoint as well as overall: below normal limit, within normal limits, and above normal limits. In the unlikely event that for a given participant, clinically significant abnormalities are noted in both directions (eg, > ULN and < LLN), then both abnormalities are counted.

The following summary tables will be created:

- Shift summary of laboratory parameters during the on-treatment period by maximum CTCAE grade;
- Shift summary of laboratory parameters from \leq Grade 2 at baseline to \geq Grade 3 post-baseline;
- Shift summary of laboratory test results with no CTCAE criteria by worst on -treatment assessment.

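### Infections are reported only as crude by-part percentages, although mean potential follow-up is about 3 months shorter in the RP2D column than in Part 1; one fixed-time table at the initial CSR would help

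*SAP*

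**What the plan says.** SAP 6.8.1.2 lists infections (the whole MedDRA system organ class), cytopenias, injection site reactions and hypogammaglobulinemia as other adverse events of clinical interest (oAECIs). For these, "A high-level summary of each oAECI will include the number and percent of participants with" any event, serious events, events by maximum grade, and so on. The only time-related output is "Time to onset of the oAECI and time to resolution of the oAECI with descriptive statistics".

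SAP 5.2 sets the columns: "All analyses will be performed by part as follows", with Part 1 and the pooled Part 2A (RP2D) + Part 2B as separate groups. SAP 3.5 runs the on-treatment period from first dose to 90 days after last dose, or to the day before new anticancer therapy if that is earlier. SAP 5.2.1 drops data after the cutoff. Treatment continues until progression or toxicity (Protocol 6.1.1).

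Kaplan-Meier methods and estimates at fixed times are planned for PFS, DOR, DOCR and OS. No person-time rate or cumulative incidence is planned for any adverse event table. Exposure is shown separately: SAP 6.7.3 gives treatment duration and "Number and percent of participants starting a cycle".

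**The concern.** A crude percentage of participants with an event grows with time observed. The parts open one after another by rule and share one cutoff, so Part 1 has had longer to accumulate infections than the later RP2D column. A colleague reading the two columns side by side at the initial CSR would tend to see fewer infections with the RP2D even if the underlying hazards were the same.

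The protocol names infection as a risk that elranatamab treatment increases (2.3.1), and describing the safety of the alternative regimens is a secondary objective. Readers are therefore likely to look at these columns. What is at stake is the interpretation of a descriptive table, not a decision rule.

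**Working it through.** The documents state no follow-up gap, so there is no figure of theirs to reproduce. The gap is built from the opening rules.

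**Inputs from the documents**
- Part 1 enrols first (Protocol 6.3.1).
- Each Part 2A dose level completes its DLT window before the next dosing decision (SAP 5.1.2.2). That window is 28 days and follows a 28-day Cycle 1 (SAP 3.2.2.1, 5.2.5).
- Part 2B opens after RP2D selection (Protocol 4.1). Dose level 2 (152 mg) was selected.
- The pooled column is 8 + 22 as planned. Eleven were actually treated in Dose level 2.
- At the initial CSR, participants have been followed for response for at least 6 months; at the final analysis the last participant has at least 2 years (SAP 6).
- One month is 30.4375 days.

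**Lag in potential follow-up, before any accrual time**
- Dose level 2: 28 + 28 = 56 days. Part 2B: 2 × 56 = 112 days.
- Pooled, planned: (8 × 56 + 22 × 112)/30 = 97.1 days = 3.19 months.
- Pooled, 11 in Dose level 2: (11 × 56 + 22 × 112)/33 = 93.3 days = 3.07 months.
- With the first higher dose 3 days early, as the visit window allows, these fall to 92 and 88 days.

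**Potential follow-up T at the initial CSR:** Part 2B 6.00 months; Dose level 2 6.00 + 56/30.4375 = 7.84; Part 1 6.00 + 112/30.4375 = 9.68.

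**Assumptions not in the documents:** an equal constant infection hazard h of 0.03, 0.06 or 0.10 per month in all parts; exponential discontinuation at rate d; and a window that closes at last dose (w = 0) or 90 days later. New therapy would put the truth between the two values of w.

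One planning figure bears on d. Part 2B enrols 22 to have at least 15 treated for 2 cycles, so −ln(15/22)/(56/30.4375) = 0.383/1.840 = 0.21 per month. This is an allowance, not an observed rate. I use d from 0 to 0.21.

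**Formulas**
- For w = 0: mean on-treatment time = (1 − exp(−dT))/d; crude incidence = h/(h+d) × (1 − exp(−(h+d)T)).
- For w = 90 days (2.96 months), with τ = T − w: mean time = w + (1 − exp(−dτ))/d; crude incidence = 1 − exp(−hw) × [1 − h/(h+d) × (1 − exp(−(h+d)τ))].
- For d = 0: crude incidence = 1 − exp(−hT).

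Example, h = 0.06 and d = 0: Part 1 is 1 − exp(−0.581) = 44.1%. Dose level 2 is 37.5% and Part 2B 30.2%, so the pooled column is (8 × 37.5 + 22 × 30.2)/30 = 32.2%.

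**Initial CSR, 8 + 22**

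| d per month | Tail | Mean months on treatment, Part 1 vs RP2D column (gap) | RP2D column low by, for h = 0.03 / 0.06 / 0.10 |
|---|---|---|---|
| 0 | any | 9.68 vs 6.49 (3.19) | 7.5 / 11.9 / 14.4 points |
| 0.08 | 0 | 6.74 vs 5.05 (1.69) | 4.0 / 6.3 / 7.7 |
| 0.08 | 90 d | 8.16 vs 6.02 (2.14) | 5.1 / 8.0 / 9.8 |
| 0.21 | 0 | 4.14 vs 3.53 (0.61) | 1.5 / 2.3 / 2.8 |
| 0.21 | 90 d | 6.56 vs 5.42 (1.14) | 2.7 / 4.3 / 5.3 |

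With 11 + 22 each figure is slightly smaller (for example 13.8 in place of 14.4).

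**Final analysis** (T = 27.68, 25.84 and 24.00 months): 2.4 to 4.4 points at d = 0, 0.3 to 0.7 at d = 0.08, and under 0.1 at d = 0.21.

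**Fixed-time check:** Day 168 is 168/30.4375 = 5.52 months, inside the 6-month minimum. Under the same model the Day 168 cumulative incidence is identical in both columns: at h = 0.06, 28.2% with d = 0 and 23.1% with d = 0.08 and no tail.

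**Noise:** the SE of the crude difference, √(p₁(1−p₁)/30 + p₂(1−p₂)/30), is about 8 to 13 points over this grid. Chance would reverse the sign in about 13 to 43% of cases.

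**The case against.** **No planned use is harmed.** The parts are non-randomized, Protocol 9.3.1 rules out formal testing, and the safety objective is to describe, not to compare. This stands. A reader might infer that the tables could steer the RP2D choice or a hold. The documents do not support that: the RP2D was chosen in a dose level review before Part 2B, and the hold rules do not use these summaries.

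**Time-based views already exist.** This stands in part. For laboratory data, "Abnormalities will be described using the worst grade by scheduled timepoint and overall", and for visit-specific analyses "percentages will be based on the number of participants still present in the study at that visit". Onset of adverse events of special interest, which include peripheral neuropathy, is "as well as broken down in categories by the time to onset and resolution of the AESI". A reader might infer that hypogammaglobulinemia is left uncovered because Protocol Table 14 names no immunoglobulins. That goes too far. Serum IgG, IgA and IgM are measured every 28 days in all participants, whether or not a dose is given (Protocol 1.3.1, 1.3.2, 8.1.1). SAP 6.8.3 presents results outside CTCAE by scheduled timepoint and can be read to include them, although it does not name them. None of these views covers infections. Time to onset describes only participants who had an event.

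**Three months is not the difference in time at risk.** This stands. It is a weighted mean of potential follow-up. The minimum lag for a Dose level 2 participant is 56 days (1.8 months), and discontinuation shrinks the realized gap.

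**The hazard may not be constant.** This stands. At the initial CSR all potential follow-up covers Cycles 1 to 6, so Part 1's extra time falls after Cycle 6, when responders move to less frequent dosing. A lower hazard there would shrink the artefact.

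**A better statistic does not make the parts comparable.** This also stands. Prophylaxis guidance changed between amendments, and allocation is not random.

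**Conclusion.** The point holds for infections, as a reporting weakness of modest and uncertain size. The direction follows from the enrolment order; the size rests on assumed hazards and discontinuation. At the initial CSR the realized gap is about 0.6 to 3.2 months, and the RP2D column would read about 1.5 to 14 points low under equal hazards. The upper end requires that nobody discontinues, which is unlikely for treatment given until progression. At the final analysis the artefact is about 0 to 4 points. With about 30 participants per column it can be hidden or reversed by chance.

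A reader might infer that the RP2D will be shown as safer than it is. The documents do not support so firm a statement. They support only that crude percentages are the wrong statistic to set side by side here, and that a better one can be had from data already collected.

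**What to change.** At the initial CSR, add one by-part table for infections and Grade 3 or higher infections:

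1. Cumulative incidence at Day 168 (end of Cycle 6), with end of the on-treatment period as the competing end and censoring at data cutoff.
2. First events per 100 participant-months at risk, with 95% CI.

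Footnote that crude percentages are not comparable across parts, that the parts are non-randomized, and that prophylaxis guidance changed over time. Including hypogammaglobulinemia adverse events is optional; stating in SAP 6.8.3 that immunoglobulins are summarized by scheduled timepoint would serve as well.

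The cost is one table from adverse event, dosing and cutoff dates already collected; no endpoint or decision rule changes. The downsides are wide intervals (8 of 30 gives an exact 95% CI of 12 to 46%; 8 first events in 150 participant-months gives 5.3 per 100, CI 2.3 to 10.5), no count of events after Day 168 in item 1, a roughly constant hazard assumed in item 2, and no correction for calendar-time changes or non-random allocation.

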6.8.2. Deaths

The frequency (number and percentage) of participants in the Safety Analysis Set who died at any time and who died within 90 days after last dose of study intervention as well as the primary and secondary reason for death, will be tabulated based on information from the 'Death Details' and 'Survival Follow-Up' CRFs.

Date and cause of death will be provided in individual participant data listing together with selected dosing information (study intervention received, date of first/last administration, dose).

In addition, deaths due to COVID-19 may be presented in a separate listing if there is significant impact of COVID-19.

6.8.3. Laboratory Data

Laboratory results will be converted to International System of Units (Système International d'unités, SI) units which will be used for applying toxicity grades and for all summaries.

As described in [Section 3.4](#), baseline will be defined as the last assessment performed on or prior to date of the first dose of study intervention. If there are multiple assessments that meet the baseline definition on the same day without the ability to determine which was truly last, then the worst grade will be assigned as the baseline grade.

Results collected as strict inequalities (eg, >10 , <10) will be converted to numeric values adding or subtracting a factor of $<0.001>$. Expressions of the form “ \geq ” or “ \leq ” will be converted to the end point. These numeric values will be evaluated for clinically significant abnormalities, but will not be included in calculations of summary statistics except for efficacy related laboratory results. Additional data handling rules for efficacy related laboratory data will be described in the programming plan.

Additionally, laboratory results will be programmatically classified according to NCI-CTCAE version 5.0 grade. Non-numerical qualifiers will not be taken into consideration in the derivation of grade (eg, hypokalemia Grade 1 and Grade 2 are only distinguished by a non-numerical qualifier and therefore Grade 2 will not be derived). In summary statistics the number and percentage of participants corresponding to grades that only include non-quantitative criteria will be displayed as a blank or NA (not assessed) rather than 0. If there is any overlap between grade criteria (eg, CTCAE grading criteria for Creatinine Increased – a value can fall into one range based on comparison to Upper Limit of Normal (ULN) and another range based on comparison to baseline), the highest (worst) grade would be assigned to that record. Grade 5 is defined in the CTCAE criteria guidance as an event with an outcome of death. Since laboratory data does not collect an outcome, Grade 5 is not used when programmatically grading laboratory data.

For laboratory tests without CTCAE grade definitions, results will be categorized as normal, abnormal, or not done.

Grade 0 or Outside Toxicity Reference (OTR) is not defined specifically in the CTCAE guidance. However, programmatically this is used as a category to represent those participants who did not meet any of the Grades 1 to 4 criteria. If the laboratory value is evaluable for CTCAE criteria grading (numeric value is present, valid units and ranges are present as required to allow conversion to standard units and grading), and does not qualify for any of the Grade 1-4 criteria for a given lab test, then the value is assigned as Grade 0 or OTR.

Several of the CTCAE terms (including Hypo/Hypercalcemia, Chronic Kidney Disease, and Activated Partial Thromboplastin) can be derived using several laboratory tests (analytes) as follows:

- Hypo/Hypercalcemia – graded by Serum Calcium or Ionized Calcium;
- Chronic Kidney Disease – graded by estimated Glomerular Filtration Rate (eGFR) or Creatinine Clearance;
- Activated Partial Thromboplastin Time Prolonged (aPTT) – graded by Partial Thromboplastin Time (PTT) or activated Partial Thromboplastin Time (aPTT).

For WBC differential counts (total neutrophil [including bands], lymphocyte, monocyte, eosinophil, and basophil counts), the absolute value will be used when reported by the lab and will be graded following the CTCAE guidance.

When only percentages are available (this is mainly applicable for neutrophils and lymphocytes, because the CTCAE grading is based on the absolute counts), the absolute value is derived as follows:

$$\text{Derived differential absolute count} = (\text{WBC count}) \times (\text{Differential \%value} / 100)$$

If the investigator reports both the absolute and % value for Neutrophils or Lymphocytes from the same laboratory sample date and participant, ONLY the absolute value will be graded. The % value will not be graded in this scenario.

If the % value is converted to the differential absolute count for grading and the Lower Limit of Normal (LLN) for the differential absolute count is not available (only LLN for % is available) then Grade 1 will be assigned if the following conditions are met:

- Lymphocyte count decreased:
 - derived absolute count does not meet Grade 2-4 criteria, and
 - % value < % LLN value, and
 - derived absolute count $\geq 800/\text{mm}^3$.
- Neutrophil count decreased:
 - derived absolute count does not meet Grade 2-4 criteria, and
 - % value < % LLN value, and
 - derived absolute count $\geq 1500/\text{mm}^3$.

For calcium, CTCAE grading is based on Corrected Calcium and Ionized Calcium. Corrected Calcium is calculated from Albumin and Calcium as follows:

$$\text{Corrected Calcium (mg/dL)} = \text{measured total calcium (mg/dL)} - 0.8 [\text{serum albumin (g/dL)} - 4]$$

Creatinine clearance is calculated as follows:

- Male: Creatinine Clearance = $((140 - \text{Age}) / (\text{Serum Creatinine})) * (\text{Weight} / 0.814)$;
- Female: Creatinine Clearance (eGFR) = $0.85 * ((140 - \text{Age}) / (\text{Serum Creatinine})) * (\text{Weight} / 0.814)$.

Note: the SI unit of Serum Creatinine is "micromol/L", the unit of weight is "Kg".

Abnormalities will be described using the worst grade by scheduled timepoint and overall. Worst case overall will be determined using laboratory results from scheduled and unscheduled visits. Several laboratory tests have bi-directional grading criteria defined so that both low (hypo) and high (hyper) values can be graded separately. Each criterion will be summarized separately. In the cases where a value is graded as a Grade 1, 2, 3, or 4 for one of the directions, that value will also be assigned as a Grade 0 for the opposite direction for that test. For example, a value meeting the criteria for Grade 3 Hypercalcemia will be classified as a Grade 0 Hypocalcemia. For CTCAE terms that can be derived using one of several laboratory tests, the maximum postbaseline grade for a given participant and CTCAE term will be the maximum across all possible laboratory tests.

Additional laboratory results that are not part of NCI-CTCAE will be presented according to the following categories by scheduled timepoint as well as overall: below normal limit, within normal limits, and above normal limits. In the unlikely event that for a given participant, clinically significant abnormalities are noted in both directions (eg, > ULN and < LLN), then both abnormalities are counted.

The following summary tables will be created:

- Shift summary of laboratory parameters during the on-treatment period by maximum CTCAE grade;
- Shift summary of laboratory parameters from \leq Grade 2 at baseline to \geq Grade 3 post-baseline;
- Shift summary of laboratory test results with no CTCAE criteria by worst on -treatment assessment.

All laboratory test results will be presented in a data listing sorted by participant identifier, laboratory test, and date/time of collection. The CTCAE grades and the classifications relative to the laboratory reference ranges will be presented. Values outside laboratory normal ranges will be flagged where appropriate.

Liver function tests: Alanine aminotransferase (ALT), aspartate aminotransferase (AST), Alkaline Phosphatase (ALP), and total bilirubin (TBILI) are used to assess possible drug induced liver toxicity. The ratios of test result over the ULN will be calculated and classified for these 3 parameters during the on-treatment period.

Summary of liver function tests will include the following categories. The number and percentage of participants with each of the following during the on-treatment period will be summarized:

- $ALT \geq 3 \times ULN$, $ALT \geq 5 \times ULN$, $ALT \geq 10 \times ULN$, $ALT \geq 20 \times ULN$
- $AST \geq 3 \times ULN$, $AST \geq 5 \times ULN$, $AST \geq 10 \times ULN$, $AST \geq 20 \times ULN$
- $(ALT \text{ or } AST) \geq 3 \times ULN$, $(ALT \text{ or } AST) \geq 5 \times ULN$, $(ALT \text{ or } AST) \geq 10 \times ULN$, $(ALT \text{ or } AST) \geq 20 \times ULN$
- $TBILI \geq 2 \times ULN$
- Concurrent $ALT \geq 3 \times ULN$ and $TBILI \geq 2 \times ULN$
- $ALT \geq 3 \times ULN$ and $TBILI \geq 2 \times ULN$ at any timepoint
- Concurrent $AST \geq 3 \times ULN$ and $TBILI \geq 2 \times ULN$
- $AST \geq 3 \times ULN$ and $TBILI \geq 2 \times ULN$ at any timepoint
- Concurrent $(ALT \text{ or } AST) \geq 3 \times ULN$ and $TBILI \geq 2 \times ULN$
- $(ALT \text{ or } AST) \geq 3 \times ULN$ and $TBILI \geq 2 \times ULN$ at any timepoint
- Concurrent $(ALT \text{ or } AST) \geq 3 \times ULN$ and $TBILI \geq 2 \times ULN$ and $ALP \geq 2 \times ULN$
- $(ALT \text{ or } AST) \geq 3 \times ULN$ and $TBILI \geq 2 \times ULN$ and $ALP \geq 2 \times ULN$ at any timepoint
- Concurrent $(ALT \text{ or } AST) \geq 3 \times ULN$ and $TBILI \geq 2 \times ULN$ and $ALP \leq 2 \times ULN$ or missing
- $(ALT \text{ or } AST) \geq 3 \times ULN$ and $TBILI \geq 2 \times ULN$ and $ALP \leq 2 \times ULN$ or missing at any timepoint.

Concurrent measurements are those occurring on the same date.

Categories will be cumulative, ie, a participant with an elevation of $AST \geq 10 \times ULN$ will also appear in the categories $\geq 5 \times ULN$ and $\geq 3 \times ULN$. Liver function elevation and possible Hy's Law cases will be summarized using frequency counts and percentages.

An evaluation of Drug-Induced Serious Hepatotoxicity (eDISH) plot will also be created by graphically displaying:

- peak serum ALT(/ULN) vs peak total bilirubin (/ULN) including reference lines at ALT=3×ULN and total bilirubin=2×ULN.
- peak serum AST(/ULN) vs peak total bilirubin (/ULN) including reference lines at AST=3×ULN and total bilirubin=2×ULN.

In addition, the following listings of all TBILI, ALT, AST and ALP values will be provided:

- For participants with a postbaseline TBILI≥2×ULN, ALT≥3×ULN or AST≥3×ULN and ALP≤2×ULN or missing at any timepoint;
- For participants with a postbaseline TBILI≥2×ULN, ALT≥3×ULN or AST≥3×ULN and ALP≤2×ULN or missing at the same visit.

